6.10.2 Serious Adverse Event (SAE)

The following criteria qualify an AE as an SAE:

Death:	An event resulting in death (including a fetal death).
Life-threatening:	In the opinion of the investigator, an event that would have resulted in immediate death if medical intervention had not been undertaken. This does not include an event that would have been fatal if it had occurred in a more severe form.
Hospitalization:	During this investigation, all patients will be hospitalized.
Prolongation of Hospitalization:	An event that prolongs the patient's stay in the hospital. By definition, this is a different event from the event that resulted in the hospitalization.
Congenital Abnormality:	An abnormality detected at or after birth in the offspring of a study patient.
Persistent or Significant Disability/Incapacity:	An event that substantially interferes with the patient's daily activities of living. This category is not intended to include events of relatively minor medical significance such as minor trauma, diarrhea, nausea, etc.
Important Medical Event:	A medically important event or reaction that may not be immediately life-threatening or result in death or hospitalization, but may jeopardize the patient or requires intervention to prevent one of the other outcomes listed above. Examples of such events include intensive treatment in an emergency room or at home for allergic bronchospasm, blood dyscrasias or convulsions that do not result in hospitalization, or development of drug dependence or drug abuse.
Abortion:	The spontaneous or induced termination of pregnancy (includes elective, induced, spontaneous and missed abortion, as well as miscarriage).

6.10.3 Adverse Drug Reaction

All noxious and unintended responses to a medicinal product that are related to any dose should be considered adverse drug reactions (ADR). The phrase "responses to a medicinal product" means that a causal relationship between a medicinal product and an AE is at least a reasonable possibility (ie, the relationship cannot be ruled out).

6.10.4 Unexpected Adverse Drug Reaction

An unexpected ADR is an adverse reaction for which the nature or severity is not consistent with the applicable product information.

6.10.5 Suspected Unexpected Serious Adverse Reaction

An AE suspected to have a causal relationship to an investigational or marketed drug and meeting criteria for seriousness and unexpectedness. Suspected Unexpected Serious Adverse Reactions (SUSARs) are also reportable for active comparator products, placebo, or the clinical study protocol itself (ie, events due to study procedures).

6.10.6 Adverse Events Related to Anticoagulation or CRRT

The anticipated adverse effects for this study have been identified in the list below.

- Air embolism
- Anemia
- Bleeding episodes
- Blood loss
- Bradycardia
- Cardiopulmonary arrest
- Coagulation of the dialyzer/extracorporeal circuit resulting in blood loss
- Cramping
- Disequilibrium syndrome
- Dizziness
- Electrolyte Imbalance
 - Hypercalcemia
 - Hypocalcemia
 - Hyperkalemia
 - Hypokalemia
 - Hypermagnesemia
 - Hypomagnesemia
 - Hypernatremia
 - Hyponatremia
 - Hyperphosphatemia
 - Hypophosphatemia
- Excessive weight loss or gain
- Filter or tubing set blood leak resulting in blood loss
- Fluid imbalance
- Hemolysis
- Hypersensitivity or Allergic Reactions "First Use Reaction"
- Hypertension

- Hypotension
- Hypothermia
- Hypervolemia
- Hypovolemia
- Infection
- Metabolic acidosis
- Metabolic alkalosis
- Nausea
- Pyrogenic Reaction
- Tachycardia
- Vomiting

6.11 Site Reporting Requirements

During the course of the study, the Investigator or designee will routinely monitor each patient for the occurrence of any AE/ADE. If an AE/ADE occurs, the Investigator or designee will complete the AE eCRF which includes the following:

- a. Description of the event
- b. Start and stop date of the event
- c. Timing of the event
- d. Seriousness of the event (yes, no)
- e. Severity of the event (mild, moderate, or severe)
- f. Causality of the event (related to treatment and/or related to the IP)
- g. Outcome of the event (fatal, not recovered/not resolved, recovering/resolving, recovered/resolved with sequelae, recovered/resolved, and unknown)

All SAEs must be reported to the Baxter Global Patient Safety (GPS) within 24 hours of the Investigator or designee becoming aware of its occurrence. The initial 24-hour reporting requirement can be met by using either the electronic SAE eCRF or the paper SAE form. The informed site team member should also contact their site monitor by phone or email to notify him/her of the event. This requirement is irrespective of whether the AE is thought to be possibly related to the study product or not. After the initial 24-

hour reporting, both the Baxter electronic SAE eCRF and the paper SAE report form must be completed for all SAEs. The paper SAE report form is to include copies of documents (de-identified) requested within the form (if applicable). The paper SAE forms should be sent by email to:

In case this email is down, the site must notify GPS by fax: Once received, the SAE report will be reviewed for completeness and forwarded on to the Medical Monitor and Baxter Global Patient Safety within 1 calendar day of receipt.

Follow-up or new information about a SAE should be provided by the investigator/designee using the paper SAE form within 24 hours of becoming aware of the new information. If the follow-up or new information impacts any of the fields in the electronic SAE eCRF the SAE eCRF should be updated within 24 hours of becoming aware of the new information.

If the Investigator suspects the SAE could possibly be a SUSAR, the following should also be contacted as soon as possible:

:
, MD
Baxter Healthcare Corporation
[name]
Tel:
Email:
Other Contacts: , MS
Baxter Healthcare Corporation
Mobile:
Email:
, BSN, RN

Baxter Healthcare Corporation
[name]
Tel: _____ / Mobile: _____
Email:

Serious Adverse Events will be reviewed and causality assessment will be completed by Baxter.

6.11.1 Sponsor to FDA/ and Investigator to IRB/Ethics Committee

Baxter will assess each SAE reported by the Investigator to determine if the SAE qualifies as an Expedited Report according to FDA and/or criteria. Per regulations, Investigators will receive a letter from Baxter describing the SUSAR. The Investigator should file this letter within their Investigator Study Binder. Additionally, the Expedited Report letter should be submitted by the Investigator to their IRB/REB, as appropriate per FDA or regulations.

6.12 Concomitant Therapy

The Investigator should review any additions or changes in concomitant therapy. All medications should be recorded in the source documents or equivalent. Prior medications, defined as those taken and/or prescribed during the 7 day window prior to informed consent and those relevant to ICU admission, will be recorded on the eCRF. Concomitant medications, including dose, frequency, start and stop dates, and indication for use, will be recorded on the eCRF throughout the study.

6.13 Restrictions

Diet, Patient Activity or Concomitant Medication restrictions are not noted.

Systemic heparin or other systemic anticoagulants are prohibited.

6.14 Treatment Compliance

The facility nurse will fill out a treatment record for each study treatment, including CRRT start time, stop time, etc. Data from that record will be transcribed and submitted on eCRFs.

7. STUDY ACTIVITIES

7.1 Training on the Administration of Prismocitrate 18

The clinical sites will be required to be current users of Prismaflex Device Platform and users of citrate as an anticoagulant for CRRT circuits. The end users at these sites are authorized to use of the CRRT machines and regional citrate anticoagulation at their

institutions. Additional training on the administration of Prismocitrate 18 will be provided by the Sponsor. At the completion of training the site investigator and other end users (as delegated by an investigator) will complete an Evaluation (refer to 1407-004 Protocol Training Assessment 2015May26). Additional assessment materials for specific end user groups may be provided as needed or as determined by an investigator.

7.2 Consenting and Screening Period

Study procedures can only begin after the site has fully consented the subject. The data collection points listed in Section 7.3 will be collected during the screening period (after consent and prior to randomization). Subjects may screen up to 96 hours prior to randomization. It is anticipated that most study subjects will screen and randomize in a 24 hour period.

If any of the data points listed in Section 7.3 were collected prior to consenting the subject (within 96 hours) as standard-of-care, the site staff may enter those data points from the patient's chart into the eCRFs. The exception is Clinical laboratory evaluations which must be within 24 hours.

7.3 Patient Information to be Collected Prior to Initiation of Treatment

The following data will be collected and recorded on the eCRFs for each patient prior to treatment.

- 1. Signed Patient Informed Consent Form.
- 2. Patient Identification Number as assigned by the system.
- 3. Inclusion/Exclusion Criteria.
- 4. Patient Demographics.
 - a. Gender.
 - b. Illness severity score using the Acute Physiology and Chronic Health Evaluation (APACHE II) classification system.[15,16]
 - c. Chronological age.
 - d. Body measurements: weight, height, BMI (kg/m²).
 - e. Race.
 - f. Ethnicity.
- 5. Patient Medical Information.
 - a. Indication for CRRT*.

- * If Indication for CRRT is AKI, specify cause.
- b. Known allergies.
- c. Current medications and those prescribed during the 7-day window prior to informed consent and those relevant to ICU admission.
- d. Medical history past/present conditions as well as surgical procedures.
- e. Physical examination.
- f. Vital signs.
- g. Clinical laboratory evaluations as specified in Appendix 1.

7.4 Treatment Period

The following data will be collected and recorded on the eCRFs for each patient following randomization.

7.4.1 Treatment Information

- 1. Date & time patient randomized and treatment arm.
- 2. Date & time study CRRT initiated and discontinued.
- 3. Prismaflex M150 Set to include:
 - a. Sequential number for Prismaflex M150 Set.
 - b. Date & time of installation.
 - c. Date & time for start and end of study CRRT for each Prismaflex M150 Set.
 - d. Prismaflex M150 Set lot number (Prismaflex M150 Set must be used).
- 4. Blood access information.
 - a. Catheter-type, manufacturer, length & size.
 - b. Catheter anatomical insertion location.
- 5. Prismaflex System serial number (to confirm that only Prismaflex System is used in this study).
- 6. Treatment Modality.
 - a. Continuous venovenous hemodiafiltration (CVVHDF) confirmation.

7.4.2 Treatment Prescription – initial and all changes during Treatment Period

1. Patient fluid removal flow rate (mL/hour).

- 2. Post-filter replacement flow rate (mL/hour).
- 3. Blood flow rate (mL/minute).
- 4. Dialysate flow rate (mL/hour).
- 5. Prismocitrate 18 flow rate (mL/hour).
- 6. Calcium Gluconate or calcium chloride infusion details: dilution and rate (mL/hour).

7.4.3 Dialysate Used

- 1. Formulation.
- 2. Brand name/Manufacturer.

7.4.4 Replacement Solutions Used

- 1. Formulation.
- 2. Brand name/Manufacturer.

7.4.5 Priming Solution

- 1. Formulation.
- 2. Brand Name/Manufacturer.

7.4.6 Calcium Gluconate or Calcium Chloride

- 1. Formulation.
- 2. Brand name/Manufacturer.

7.4.7 Extracorporeal Circuit (Prismaflex M150 Set) Information

- 1. Reason (including date and time) for treatment termination (ie, clotting, increased TMP, patient required treatment/diagnostic tests external to ICU, device malfunction, etc).
- 2. Visual assessment of extracorporeal circuit at time of treatment termination due to:
 - a. Clotting in the Prismaflex M150 Set (ie, clotting in filter and blood tubing),
 - b. Clotting in the blood access device, or

- c. Clotting in both the blood access device and the Prismaflex M150 Set.
- 3. Complications related to blood loss (bleeding or Prismaflex M150 Set clotting and replacement).
 - a. Number, location and duration of any bleeding events.
 - b. Estimated blood loss (mL).
 - c. Transfusion type (whole blood, packed cells, etc.).
 - d. Transfusion volume.
 - e Adverse events

7.4.8 Anticoagulation Information

- 1. Prismocitrate 18 (volume of Prismocitrate 18 used), or
- 2. No systemic anticoagulant.

7.4.9 Patient Clotting Parameters

- 1. Prothrombin time/international normalized ratio.
- 2. Activated partial thromboplastin time.
- 3. Platelet count.
- 4. Post-filter iCa.
- 5. The number of iCa determinations (whether the patient is on Prismocitrate or not).

7.4.10 Treatment Blood Concentration Data – According to the Sampling Schedule in Appendix 1

- 1. Blood Urea Nitrogen (BUN).
- 2. Creatinine.
- 3. Serum bicarbonate, pH and base excess.
- 4. Hemoglobin and Hematocrit.
- 5. Blood sodium, potassium, chloride, iCa (systemic and post-filter), total calcium, phosphorus, and magnesium.
- 6. Total Ca/iCa ratio.
- 7. Anion gap.

8. Liver function tests (AST, ALT, ALP, Total Bilirubin) – based on local standard-of-care.

7.4.11 Fluid Balance and Hemodynamic Parameters

- 1. Total fluid input and output volume (including dialysate, replacement fluid, and effluent).
- 2. Daily patient weights recorded each morning (eg, 8:00 am) for calculation of delivered CRRT dose.
- 3. Post-treatment weight when study CRRT is terminated.
- 4. Blood pressure including mean arterial pressure at randomization and at 6 hour intervals (± 1 hour) up to End of Treatment or 120 hours of study CRRT post-randomization and at 120 hours or end of Evaluable Period.

7.5 End of Treatment or Early Termination Procedures

The following End of Treatment information will be collected and procedures or evaluations will be performed after completion of study CRRT during the Treatment Period (up to 120 hours of study CRRT):

- Physical exam including weight.
- Vital signs.
- Adverse events/serious adverse events (if not previously reported).
- Concomitant medications.
- Clinical laboratory evaluations as specified in Appendix 1.
- Bleeding events (if not previously reported).
- Transfusions (if not previously reported).
- Disposition post-study CRRT Treatment Period.

If a patient discontinues from the study prematurely, every attempt should be made to perform all of the End of Treatment procedures and evaluations. Upon exiting the study, the patient will be treated per standard-of-care, which may or may not include continued CRRT.

7.6 End of Study Procedures

After completion of study CRRT during the Treatment Period (up to 120 hours of study CRRT) AE/SAEs will be followed for a period of 30 days. All patients who complete up to 120 hours of study CRRT and the 30-day AE/SAE follow up period will successfully complete the study. Related AEs and SAEs will be followed post-study until resolution or stable.

8. PLANNED STATISTICAL METHODS

8.1 General Considerations

Unless otherwise specified, treatment effects will be evaluated on the basis of a 2-sided significance level of 0.050 (when rounded to 3 decimal places). Unless otherwise noted, all analyses will be performed using Statistical Analysis Software (SAS®), SAS/GRAPH® and SAS/STAT® software, Version 9.2 of SAS for Windows, copyright © 2002-2008 SAS Institute Inc., on a Microsoft Windows Server. SAS and all other SAS Institute Inc. product or service names are registered trademarks or trademarks of SAS Institute Inc., Cary, NC, USA.[17]

Further details of the planned statistical methods presented below will be provided in the study statistical analysis plan (SAP). The purpose of the SAP is to further elaborate the statistical methods described in the protocol and to describe analysis conventions to guide the statistical programming work. The SAP will be drafted prior to enrollment of the first patient and will be finalized prior to database soft lock in accordance with Baxter standard operating procedures.

8.2 Determination of Sample Size

A sample size of 80 patients in each treatment group will provide > 90% power for assessing the equality of the extracorporeal circuit life between treatment groups using a two-sided clustered log-rank test with an overall alpha level of 0.050. This is based on the following assumptions: median circuit lives of and respectively in the Prismocitrate and Control group, filters per patient (during the Treatment Period of 120 hours) in the Prismocitrate and Control group, respectively, of subjects discontinuing therapy for reasons other than due to clotting of the circuit (ie, common exponential dropout rate of), a single interim analysis when 50% of patients have completed treatment, and combination of results from the two study stages (prior to vs after interim analysis) using Fisher's combination test.[18]

8.3 Analysis Populations

The Full Analysis (FA) Set will include all randomized patients who received any study treatment for any period of time.

All analyses will be performed on the FA Set unless otherwise noted.

In addition to the FA Set, a Per Protocol (PP) Set will be used to check the robustness and validity of the primary analysis by repeating the analysis on the PP Set as a sensitivity analysis.

The PP Set defines a subset of the FA Set including patients who:

- fulfill all inclusion criteria.
- do not meet any of the exclusion criteria.
- were randomized and treated according to the randomization scheme.
- received at least 80% of their prescribed CRRT dose.
- do not have major protocol deviations that might impact the assessment of the primary endpoint (eg, mechanical malfunction of the machine).
- have available survival data for extracorporeal circuit life of at least one circuit
 (ie, time to occurrence of Prismaflex System alarms/conditions as outlined in
 Section 6.7.1 Primary Efficacy Endpoint and alarm cause determined and
 confirmed by Independent Adjudicator as outlined in Section 9.9 Primary
 Endpoint Adjudication, or censored circuit life if no system alarms/conditions
 occurred until the circuit was used for 72 continuous hours or if CRRT was
 stopped during the Treatment Period for reasons other than system
 alarms/conditions or if Independent Adjudicator did not confirm the alarm cause).

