1.2 Benefits and Risks for the Study Population

Since RCA has been demonstrated in controlled trials to decrease the risk of bleeding in comparison to heparin, participating patients may benefit in this respect.[9,10] Moreover, the patient's participation may demonstrate clinical benefits associated with RCA's ability to increase delivery of the prescribed CRRT dose (relative to no anticoagulation).

Foreseeable risks for the patients receiving Prismocitrate 18 mainly pertain to the changes that may occur in electrolyte and acid-base balance in association with RCA. However, specific aspects of the protocol are designed to mitigate these risks. The main risk to the Control Group in which no anticoagulation will be used is shortened filter life due to filter and extracorporeal circuit clotting, potentially resulting in patient blood loss and a lower delivery of the prescribed dose of CRRT due to more frequent treatment interruptions.

Foreseeable risks related to the use of the Prismaflex® System for Prismocitrate 18 treatment include operational errors related to patient preparation, line or bag connections, machine settings, bag handling, and bag contents. These risks have been addressed within the study protocol, investigator brochure, operator manuals, and training. Additionally, these risks will be minimized with the inclusion of the training assessment secondary endpoint by which user groups will be trained on the use of Prismocitrate 18 in CRRT and their understanding will be assessed prior to their use of the Prismaflex® System for Prismocitrate 18 treatment in the clinical trial setting. These risks will undergo monitoring and mitigation activities throughout the duration of the study.

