- For measurement of delivered dose, daily effluent volume (in mL) will be recorded from the Prismaflex System history screen. In the Prismaflex software, the starting time for the charting interval will be set (eg, at 8:00 am) and the volumes and doses will be stored for each day starting at that time. The effluent volume together with the patient's weight will be used to calculate delivered dose (mL/kg/hour). Note that *daily* weight will need to be obtained and recorded/entered each morning (eg, at 8:00 am) in the "System Tools" screen for determination of both prescribed and delivered dose as part of standard clinical practice for each patient receiving CRRT.
- For both study arms Systemic ionized blood calcium concentrations will be measured at baseline and initiation, 1 hour after initiation of CRRT (post-randomization) and then at 6 hour intervals up to 120 hours of CRRT (see Appendix 1).
 - For the Prismocitrate 18 Arm, the systemic ionized calcium must be measured 1 hour prior to the initiation of study CRRT. If initiation ionized calcium is less than 0.9 mmol/L, the investigator must correct the serum level to greater

than 0.9 mmol/L in order to begin CRRT. This corrected systemic ionized calcium will be considered the patient's initiation value (see Appendix 1).

- For Prismocitrate 18 Arm Only Post-filter blood iCa will be measured 1 hour after initiation of CRRT (post-randomization) and then at 6 hour intervals up to 120 hours of CRRT (see Appendix 1).
- Blood total calcium concentrations will be measured at baseline, initiation, 1 hour and every 6 hours during the 120 hour Treatment Period and at 120 hours or end of the Treatment Period from the initiation of study CRRT in each. In conjunction with simultaneous systemic iCa concentrations, the total calcium/iCa ratio (both measurements in mmol/L) will be determined (see Appendix 1).
- Serum electrolytes (sodium, potassium, chloride, phosphate, and magnesium, anion gap) and base excess will be measured at baseline, initiation and at 6 hour intervals of study CRRT (post-randomization) up to 120 hours (see Appendix 1).
- Blood urea nitrogen (BUN) and serum creatinine measurements will be measured at baseline, initiation and twice daily (post-randomization) up to 120 hours of study CRRT (see Appendix 1).

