5.2.2.2.1 Effluent Rate

Total effluent rate (Q_E) (mL/hour) = Pre-blood pump (PBP) infusion rate (Q_{PBP}) + Post-dilution replacement fluid rate (Q_R) + Dialysate rate (Q_D) + patient fluid removal rate (Q_{FR}) .

- QPBP corresponds to the infusion rate of Prismocitrate 18.
- As specified in the Prismaflex M150 Set IFU, post-filter replacement fluid should be prescribed according to institutional practice for proper functioning of the deaeration chamber. The use of a calcium-containing post-dilution solution is not recommended.
- To calculate the hourly effluent rate to be prescribed, assume the effluent rate is a surrogate for the daily CRRT dose and the minimum prescribed dose is 25 mL/kg/hour with a minimum target delivered dose of 20 mL/kg/hour per 24 hours dose of treatment for both groups.
- The required effluent rate (mL/hour) can then be calculated by multiplying the patient weight (in kg) at the time of CRRT initiation by the target prescribed dose.
- For example, a 90 kg patient would require a total effluent rate of 2,250 mL/hour (90 kg x 25 mL/kg per hour). While adjustments in the infusion rates of Prismocitrate 18, post-dilution replacement solution, and dialysate can be titrated to meet the desired metabolic and anticoagulation requirements for the patient, the total effluent rate should not appreciably change, with maintenance of a minimum prescribed dose of 25 mL/kg/hour.

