8.5.2 Secondary Efficacy Endpoints

A descriptive summary of systemic and post-filter blood iCa concentrations as assessed baseline (systemic only), initiation (systemic only), 1 hour and every 6 hours from the initiation of study CRRT during the 120 hour Treatment Period and at 120 hours or end of the Treatment Period will be provided by treatment group. Post-filter blood iCa concentrations will only be presented for the Prismocitrate 18 Arm.

A mixed-effects model repeated measures (MMRM) analysis will be used to evaluate differences between treatment groups in the change from initiation of study CRRT in systemic iCa concentrations that are collected 1 hour and every 6 hours from the initiation of study CRRT during the 120 hours Treatment Period and at 120 hours or end of the Treatment Period. If justified, separate models will be carried out for patients who did and did not receive standard-of-care CRRT.

In addition, frequencies and percentages will be provided for systemic iCa < 1.1 mmol/L by time point and treatment group (threshold indicative of decrease in iCa despite adequate calcium compensation).

A descriptive summary of the daily delivered dose and overall delivered dose will be provided by treatment group. Differences between treatment groups in the percentage of overall prescribed dose actually administered will be assessed on a 5% significance level using a two-sided t-test or Wilcoxon rank sum test, as applicable. However, the statistical test will only be carried out conditional upon a significant test result for the primary endpoint at the time point of the interim analysis or final analysis. This hierarchical test procedure guarantees that the overall type 1 error is controlled and preserved at a maximum of 5%.

Secondary Efficacy Endpoints will be analyzed on the FA Set based on the randomized treatment groups (intent-to-treat principle).

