If one of the rate is missing, effluent rate will not be able to calculate.

The prescribed dose (effluent rate) is calculated as:

Prescribed Effluent Rate = Body Weight \times 25 mL/kg/hr

If there are multiple records of effluent rate per day (e.g. due to infusion rate change) the average value will be used to calculate the delivered dose for that day.

The percentage of the prescribed dose actually administered to the patient will be calculated by dividing the actual effluent rate by the prescribed effluent rate. Differences between treatment groups in the percentage of overall prescribed dose actually administered will be assessed on a 5% significance level using a two-sided t-test or Wilcoxon rank sum test, as applicable. However, the statistical test will only be carried out conditional upon a significant test result for the primary endpoint at the time point of the interim analysis or final analysis. This hierarchical test procedure guarantees that the overall Type I error is controlled and preserved at a maximum of 5%.

The analysis of secondary efficacy endpoints will be carried out on the FA based on the randomized treatment groups (intent-to-treat principle).

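### The Per Protocol Set's 80%-of-dose rule selects on a consequence of clotting, so under the volume-based dose the robustness check of the primary result leans toward no difference

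*Protocol*

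**What the plan says.** Protocol 8.3 states that "a Per Protocol (PP) Set will be used to check the robustness and validity of the primary analysis". One entry condition, repeated unchanged in SAP 6.2.2, is that the patient "received at least 80% of their prescribed CRRT dose". The other conditions cover eligibility, treatment as randomized, absence of major deviations affecting the primary endpoint, and circuit-life data for at least one circuit.

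The documents link delivered dose to clotting. Protocol 1.2 names, as a risk of unanticoagulated circuits in Control, "a lower delivery of the prescribed dose of CRRT due to more frequent treatment interruptions". Protocol 8.5.2 treats the same quantity as an efficacy outcome: "Differences between treatment groups in the percentage of overall prescribed dose actually administered will be assessed on a 5% significance level".

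Dose is measured in two ways:
- **By volume.** Protocol 5.2: "daily effluent volume (in mL) will be recorded from the Prismaflex System history screen", which with body weight gives delivered dose. SAP 5.5.2 agrees.
- **By rate.** SAP 13.3 sums the component flow rates to an effluent rate. If a day has several records, "the average value will be used to calculate the delivered dose for that day". The percentage of prescribed dose is "calculated by dividing the actual effluent rate by the prescribed effluent rate", the denominator being weight times 25 mL/kg/h.

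Neither document says which measure decides entry to the PP Set.

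**The concern.** The selection variable arises after randomization and lies downstream of the primary event. When a circuit clots, treatment stops, the set is replaced, and no effluent accrues meanwhile. A patient whose circuits clot often therefore collects many primary events and a low delivered dose. An entry rule on dose removes such patients, and if Prismocitrate works there are more of them in Control. The remaining Control patients clot more slowly than Control as randomized, and the contrast shrinks.

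At stake is the reading of the PP analysis. In a trial whose primary test is significant, a weaker or non-significant PP result would normally raise doubt about robustness. Here it might reflect only the selection rule.

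**Working it through.** **1. The plan's own figures.** The minimum prescribed dose is 25 mL/kg/h, and 0.80 × 25 = 20 mL/kg/h. This equals the "minimum target delivered dose of 20 mL/kg/hour per 24 hours dose of treatment for both groups" (Protocol 5.2.2.2.1), so the 80% has a basis in the protocol. The stated power of more than 90% cannot be reproduced because its inputs are blacked out in the public copy; that is no fault of the plan.

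**2. When clotting alone fails a patient (volume-based dose).** Over 120 h, 80% is lost after 0.20 × 120 = 24 h off circuit: 4 changes at 6 h, 6 at 4 h, or 8 at 3 h. Put generally, run/(run + downtime) ≥ 0.8 requires a mean circuit run of at least 4 × downtime, ignoring that the last circuit has no downtime after it. That is 4, 8, 16 and 24 h for downtimes of 1, 2, 4 and 6 h.

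**3. Effect on the comparison (simulation).** Assumed, because the documents give no value: median circuit lives, downtime per change, and between-patient variation in clotting rate (gamma frailty, mean 1).

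*Model A:* medians 20 h (Control) and 40 h (Prismocitrate), frailty variance 0.3, fixed downtime, no other circuit stops, delivered share = running time/120 h. The ratio is Control/Prismocitrate clots per circuit-hour. Ranges cover repeated runs.

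| Downtime per change | Control qualifying | Prismocitrate qualifying | Ratio, all patients | Ratio, PP | PP trials with p<0.05, 80 per arm |
|---|---|---|---|---|---|
| 2 h | 98% or more | 100% | 1.96-1.99 | 1.92-1.96 | 100% |
| 4 h | 88% | 99% | 1.97-1.98 | 1.66-1.68 | 99% |
| 6 h | 71-72% | 94% | 1.96-1.97 | 1.46-1.47 | 86% |

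Adding circuit changes for reasons other than clotting excludes more patients and takes the PP ratio at 4 h to about 1.6, hence the stated ranges of 1.6-1.7 at 4 h and 1.4-1.5 at 6 h.

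*Model B:* medians 20 and 45 h, frailty variance 0.5, non-clotting stops (mean 80 h), dropout (mean 300 h), variable downtime, delivered share = running/elapsed time; 300 trials of 80 per arm. The ratio here is Prismocitrate/Control, and z is from a cluster-robust log-rank test.

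| Mean downtime | Control lost | Prismocitrate lost | Ratio, FA to PP | \|z\|, FA to PP |
|---|---|---|---|---|
| 1 h | 1% | 0% | 0.44 to 0.45 | 4.7 to 4.6 |
| 2 h | 8% | 3% | 0.45 to 0.48 | 4.6 to 4.1 |
| 4 h | 25% | 13% | 0.45 to 0.50 | 4.5 to 3.5 |
| 6 h | 38% | 23% | 0.45 to 0.50 | 4.6 to 3.1 |

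On Model A's scale, 4 h gives 1/0.45 = 2.2 falling to 1/0.50 = 2.0, a smaller shift. The least favourable of the larger-effect cases run (medians 12 and 30 h, frailty variance 1.0, 6 h) loses 46% of Control and 29% of Prismocitrate; the ratio moves from 0.43 to 0.55, and the chance of p<0.05 falls from about 100% to 55%. With equal medians of 20 h, exclusions are equal, the ratio stays near 1.0 and rejection stays near 5%.

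**4. The two dose definitions.** Take the protocol's 90 kg example: 90 × 25 = 2,250 mL/h. Suppose the circuit runs at that rate for 18 of 24 h.
- Volume: 18 × 2,250 = 40,500 mL; 40,500/(24 × 90) = 18.75 mL/kg/h; 18.75/25 = 75%, below the threshold.
- Average recorded rate, if off-circuit hours yield no record: 2,250/2,250 = 100%, above it.

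The same patient fails one definition and passes the other. The fixed denominator matters too, since 25 is a minimum prescription. At flows 1.2 times the denominator, the volume figure becomes 1.2 × 75% = 90%, and Model B's Control loss at 2, 4 and 6 h falls to 1%, 9% and 18%.

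**The case against.** The strongest reply is that SAP 13.3 holds the only explicit formula for percentage of prescribed dose, and SAP 11 sends the exposure analysis there. Averaged flow rates need not count downtime, so the selection may hardly occur. This stands as a real dependency. It does not rescue the criterion, because under that formula the rule no longer detects interrupted treatment.

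Second, the primary test uses the FA Set as randomized, and SAP 13.2 adds four informative-censoring scenarios on the FA. That is correct and limits the point to one supportive analysis. Those scenarios address censoring, however, not selection on dose.

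Third, a bias toward no difference is conservative. A reader might infer that agreement between PP and FA is also uninterpretable. The documents do not support that: a PP result that agrees despite the attenuation remains supportive, and the equal-median runs show no excess of false positives. Only a weaker PP result is ambiguous.

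Fourth, 80% matches the protocol's minimum target delivered dose and is the PP Set's only explicit exposure criterion. That is a fair reason for the sponsor to want it kept, and the fix allows for it.

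Finally, it is tempting to say that the rule certainly drops the worst Control patients. Fast-clotting Prismocitrate patients are dropped too, though fewer, and with short downtime almost nobody is lost.

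**Conclusion.** The concern holds, confined to the PP sensitivity analysis and conditional on the volume-based dose. Under that definition the PP Set is selected on a consequence of the primary event, more strongly in Control when treatment works, and the PP comparison is attenuated. In Model A the attenuation is negligible at 1 to 2 h of downtime per change and material from about 4 h. It is smaller under Model B and larger with short Control circuit life combined with strong frailty. Direction follows from the documents; size does not, because downtime is not stated, the medians are redacted, and frailty and other stops are assumed. Nothing here touches the primary FA test, the overall 5% error rate or the sample size.

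**What to change.** In Protocol 8.3 and SAP 6.2.2, define the PP Set for the primary-endpoint robustness check without the 80%-of-dose criterion, keeping the eligibility, treated-as-randomized, major-deviation and endpoint-data criteria. Delivered dose remains a secondary endpoint.

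If the sponsor prefers to keep the criterion, report the PP analysis with and without it, state which dose definition applies, and tabulate exclusions by arm and reason. In either case, reconcile the volume-based definition (Protocol 5.2, SAP 5.5.2) with the rate-based one (SAP 13.3), since the tested secondary endpoint depends on it as well.

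Cost: a one-line change in each document, or one extra analysis run. Without the criterion, the PP Set may include some patients with low exposure for reasons unrelated to clotting.
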